### Onset of Local Reaction

The onset day of each local reaction and any local reaction will be derived.

For the onset day of each local reaction, if participants report severity change of the local reaction, the first day of initial reporting of that specific local reaction will be counted.

For the onset day of any local reaction, the first day of reporting any severity of any local reaction will be counted.

In summary, the following variables will be derived for local reactions:

1. Presence or absence of each local reaction on each day (Days 1-7) after each vaccination.
2. Presence or absence of each local reaction on “any day (Day 1-7)” after each vaccination.
3. Maximum severity of each local reaction on “any day (Day 1-7)” after each vaccination.
4. Maximum severity of each local reaction on “any day (Day 1-7)” after any vaccination.
5. Presence or absence of any local reaction on each day (Days 1-7) after each vaccination.
6. Presence or absence of any local reaction on “any day (Day 1-7)” after each vaccination.
7. Duration of each local reaction after each vaccination.
8. Onset day of each local reaction after each vaccination.
9. Onset day of any local reaction after each vaccination.

### 3.5.2.2. Systemic Events

Systemic events reported via the e-diary are fever, decreased appetite, drowsiness, and irritability for participants 1 to  $\leq$ 2 years of age; and fever, fatigue, headache, vomiting, diarrhea, muscle pain, and joint pain for participants  $>$ 2 years of age. The participant or participant’s legally acceptable representative/parent/legal guardian is to document the presence or absence of systemic events in the e-diary as “mild,” “moderate,” “severe,” or “none”. The participant or participant’s legally acceptable representative/parent/legal guardian is to be asked to assess the severity of each event according to Table 8 and [Table 9](#) below.

Only an investigator is able to classify a participant’s systemic event as Grade 4, after physical examination of the participant or documentation from another medically qualified source (eg, emergency room or hospital record) or contact with the participant. If a participant experiences a Grade 4 systemic event, the investigator must immediately notify the sponsor. A Grade 4 event will be collected on the unscheduled reactogenicity page and as an AE on the CRF. The event will be graded using the AE severity grading scale (see Section 10.3 of the protocol). Further, for all ongoing systemic events on Day 7, the stop date will be recorded in the CRF.

**Table 8. Grading Scale for Systemic Events for Participants 1 to  $\leq$ 2 Years of Age**

	Mild Grade 1	Moderate Grade 2	Severe Grade 3	Grade 4a
Decreased appetite (loss of appetite)	Decreased interest in eating	Decreased oral intake	Refusal to feed	Emergency room visit or hospitalization for severe decreased appetite (loss of appetite)

**Table 8. Grading Scale for Systemic Events for Participants 1 to  $\leq$ 2 Years of Age**

	Mild Grade 1	Moderate Grade 2	Severe Grade 3	Grade 4a
Drowsiness (increased sleep)	Increased or prolonged sleeping bouts	Slightly subdued interfering with daily activity	Disabling not interested in usual daily activity	Emergency room visit or hospitalization for severe drowsiness (increased sleep)
Irritability (fussiness) (synonymous with restless sleep; decreased sleep)	Easily consolable	Requiring increased attention	Inconsolable; crying cannot be comforted	Emergency room visit or hospitalization for severe irritability (fussiness)

a. Grade 4 assessment should be made by an investigator; Grade 4 will not be collected in the e-diary but will be collected in the case report form.

**Table 9. Grading Scale for Systemic Events for Participants  $>$ 2 Years of Age**

	Mild Grade 1	Moderate Grade 2	Severe Grade 3	Grade 4a
Fatigue (= tiredness in diaries)	Does not interfere with activity	Some interference with activity	Prevents daily routine activity	Emergency room visit or hospitalization for severe fatigue
Headache	Does not interfere with activity	Some interference with activity	Prevents daily routine activity	Emergency room visit or hospitalization for severe headache
Vomiting	1 to 2 times in 24 hours	>2 times in 24 hours	Requires intravenous hydration	Emergency room visit or hospitalization for severe vomiting
Diarrhea	2 to 3 loose stools in 24 hours	4 to 5 loose stools in 24 hours	6 or more loose stools in 24 hours	Emergency room visit or hospitalization for severe diarrhea
Muscle pain	Does not interfere with activity	Some interference with activity	Prevents daily routine activity	Emergency room visit or hospitalization for severe muscle pain
Joint pain	Does not interfere with activity	Some interference with activity	Prevents daily routine activity	Emergency room visit or hospitalization for severe joint pain

a. Grade 4 assessment should be made by an investigator; Grade 4 will not be collected in the e-diary but will be collected in the case report form.

The highest temperature for each day for 7 days after vaccination is to be recorded in the e-diary. The protocol defines fever as an axillary temperature  $\geq$ 37.5°C. For ongoing fever on Day 7, the stop date will be recorded in the CRF. For reporting purposes, fever will be analyzed using the following temperature grading scale as displayed in [Table 10](#) for all participants.

**Table 10. Ranges for Fever**

	Mild Grade 1	Moderate Grade 2	Severe Grade 3	Grade 4
Fever	$\geq 37.5^{\circ}\text{C}; \leq 38.4^{\circ}\text{C}$	$\geq 38.5^{\circ}\text{C}; \leq 38.9^{\circ}\text{C}$	$\geq 39.0^{\circ}\text{C}; \leq 40.0^{\circ}\text{C}$	$>40.0^{\circ}\text{C}$

The presence or absence of each systemic event on a given day is defined as follows:

- = “Missing,” if the value is missing on a given day;
- = “Yes,” if the participant reports a temperature  $\geq 37.5^{\circ}\text{C}$  for fever **or** “mild,” “moderate,” “severe,” or “Grade 4” for the remaining events on a given day;
- = “No,” if the participant reports a temperature  $<37.5^{\circ}\text{C}$  for fever **or** “none” for the remaining events on a given day.

For each systemic event, the following variables will be derived:

1. Presence or absence of each systemic event on each day (Days 1-7) after each vaccination.
2. Presence or absence of each systemic event on “any day (Day 1-7)” after each vaccination.
3. Maximum severity of each systemic event on “any day (Day 1-7)” after each vaccination.
4. Maximum severity of each systemic event on “any day (Day 1-7)” after any vaccination.
5. Presence or absence of any systemic event on each day (Days 1-7) after each vaccination.
6. Presence or absence of any systemic event on “any day (Day 1-7)” after each vaccination.
7. Duration of each systemic event after each vaccination.
8. Onset day of each systemic event after each vaccination.
9. Onset day of any systemic event after each vaccination.

The derivation of these variables is similar to the derivation of the variables for local reactions (Section 3.5.2.1). “Any systemic event” includes any fever, decreased appetite, drowsiness, or irritability for participants 1 to  $\leq 2$  years of age; and any fever, fatigue, headache, vomiting, diarrhea, muscle pain, or joint pain for participants  $>2$  years of age.

### 3.5.3. Use of Antipyretic/Pain Medication

Use of antipyretic and/or pain medication will be reported via the e-diary. The participant or participant's parent(s)/legal guardian(s) is to document the presence or absence of use of antipyretic and/or pain medication in the e-diary as "yes" or "no". Variables other than those related to severity are derived following the same rule as for local reactions (Section 3.5.2.1).

### 3.5.4. Physical Examination

Physical examination will be performed prior to vaccination at the first vaccination visit and will include any clinically significant abnormalities within the following body systems: general appearance; lungs; heart; abdomen; musculoskeletal; neurological; skin; and lymph nodes. Prior to subsequent vaccination (at Visits 2 and 4), physical examination will be performed if the clinical assessment indicates that it is necessary to comprehensively evaluate the participant.

## 4. ANALYSIS SETS (POPULATIONS FOR ANALYSIS)

Data for all participants will be assessed to determine if participants meet the criteria for inclusion in each analysis population prior to releasing the database and classifications will be documented per standard operating procedures. For purpose of analysis, the following populations are defined for each age group.

Population	Description
Enrolled	"Enrolled" means that a participant, or his or her legally authorized representative, has agreed to participate in a clinical study following completion of the informed consent process and is deemed eligible to participate. Potential participants who are screened for the purpose of determining eligibility for the study, but do not participate in the study, are not considered enrolled, unless otherwise specified by the protocol.
Evaluable immunogenicity	All participants who are eligible, receive all 3 doses of the investigational product, have blood drawn for assay testing within the specified time frame for baseline and 4 weeks (21-35 days) after the third vaccination, have valid and determinate assay result (NT titer) at baseline and 4 weeks after the third vaccination visit, are NT seronegative (NT titer <1:10) at baseline, and have no major protocol violations.
Evaluable immunogenicity for the second dose	All participants who are eligible, receive the first 2 doses of the investigational product, have blood drawn for assay testing within the specified time frame for baseline and 4 weeks (21-35 days) after the second vaccination, have valid and determinate assay result (NT titer) at baseline and 4 weeks after the second vaccination visit, are NT seronegative (NT titer <1:10) at baseline, and have no major protocol violations.

Population	Description
All-available immunogenicity	All enrolled participants who receive at least the first 2 doses of the investigational product and have valid and determinate assay results (NT titer CCI ) 4 weeks after the second and/or the third vaccination.
Safety	All enrolled participants who receive at least 1 dose of the investigational product.

Major protocol violations will be determined by clinical review (through the data handling memo). A major protocol violation is a protocol violation that, in the opinion of the sponsor's study medical monitor, would materially affect assessment of safety and/or immunogenicity, eg, participant receipt of a prohibited vaccine or medication that might affect immune response or a medication error with suspected decrease in potency of the vaccine. The sponsor's medical monitor will identify those participants with protocol violations before any immunogenicity analysis is carried out.

For local reactions, systemic events, fever, and use of antipyretic and/or pain medication, the definition of the denominators for the percentage calculations are described in [Section 3.5.2](#) based on e-diary record. In addition, these tables will be generated without e-diary data that have been confirmed by the participant to have been entered in error. Data-entry errors will be discussed in the clinical study report text and documented in a separate listing.

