9.4.1. Immunogenicity Analyses

Endpoint	Statistical Analysis Methods
Primary	Point estimate and the exact 2-sided 95% CI will be calculated using the Clopper-Pearson method for the seropositivity rate based on the immune response determined by NT 4 weeks after the third vaccination. NT titers $\geq 1:10$ are considered seropositive. The evaluable immunogenicity population will be the primary population for the analysis.
Secondary	Point estimate and the exact 2-sided 95% CI will be calculated using the Clopper-Pearson method for the seropositivity rate based on the immune response determined by NT 4 weeks after the second vaccination. Neutralizing antibody GMT 4 weeks after the second vaccination and 4 weeks after the third vaccination will be calculated. Two-sided 95% CIs for the mean of the logarithmically transformed assay results will be computed based on the Student t distribution. GMFRs and associated 2-sided 95% CIs will be provided for neutralizing antibody titer from baseline to 4 weeks after the second and 4 weeks the third vaccinations. In addition, GMFR will be provided for neutralizing antibody titer from 4 weeks after the second vaccination to 4 weeks after the third vaccination. The GMFR will be calculated as the mean of the difference of logarithmically transformed antibody titers (postvaccination minus prevaccination for each participant) and transformed back to the original scale. Two-sided 95% CIs will be obtained by constructing CIs using 1-sample Student's t distribution for the mean difference of measures on the logarithmically transformed assay results, and transforming the limits back to the original scale. Empirical RCDCs by time points will be presented for neutralizing antibody titer. Titers below the LLOQ or denoted as BLQ will be set to $0.5 \times \text{LLOQ}$ for analysis. The above analyses are based on the evaluable immunogenicity population. An additional analysis will be performed based on all-available immunogenicity population if there is enough difference between the all-available immunogenicity population and the evaluable immunogenicity population. Missing serology data are not imputed.

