9.5. Interim Analyses

No formal interim analysis will be conducted for this study. As this is an open-label study, the sponsor may conduct unblinded reviews of the data during the course of the study for the purpose of safety assessment, and supporting clinical development.

CCI

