## 5. GENERAL METHODOLOGY AND CONVENTIONS

All analyses will be performed after completion of the study.

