### **6.5.2. Study Conduct and Participant Disposition**

The numbers and proportions of enrolled participants will be included in the participant disposition summary. In addition, participants who completed all study procedures, and those who withdrew in the middle of the study, along with the reasons for withdrawal, will be tabulated by age group separately. The reasons for withdrawal will be those as specified in the database.

Participants excluded from the evaluable immunogenicity and all-available immunogenicity populations will also be summarized with reasons for exclusion. These summaries will be generated by age group.

For each vaccination, the numbers and proportions of participants who were vaccinated, and had blood drawn within the protocol-specified time frame, and outside the specified window, will be tabulated by age group.

The numbers and proportions of participants with e-diary data not transmitted, transmitted by day (Days 1-7), and transmitted on “all days” will be summarized by age group.

Data listings of participants who withdrew during the study will be generated. Also, data listings of participants excluded from the evaluable and all-available immunogenicity populations will be generated separately.

The protocol deviations listings will be generated.

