## **7. INTERIM ANALYSES**

No formal interim analysis is planned for this study. However, as this is an open-label study, the sponsor may conduct unblinded reviews of the data during the course of the study for the purpose of safety assessment and/or to support clinical development.

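### Does the plan leave the primary test open to exclusions made by a medical monitor who already knows the antibody titres?

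*SAP*

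**What the plan says.** The evaluable immunogenicity population (Protocol 9.3, SAP 4) carries the primary test. Most of its criteria can be checked from records: three doses, blood draws in window, valid NT results, a seronegative baseline. The last, freedom from major protocol violations, needs judgement. SAP 4 defines it so: "A major protocol violation is a protocol violation that, in the opinion of the sponsor's study medical monitor, would materially affect assessment" of safety or immunogenicity. It gives two examples: a prohibited vaccine or medication that could influence the immune response, and a medication error thought to have weakened the vaccine.

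The SAP fixes when this is done. The monitor "will identify those participants with protocol violations before any immunogenicity analysis is carried out". Set membership is assessed "prior to releasing the database and classifications will be documented per standard operating procedures". SAP 5 adds: "All analyses will be performed after completion of the study". On reporting, SAP 6.5.2 says: "Participants excluded from the evaluable immunogenicity and all-available immunogenicity populations will also be summarized with reasons for exclusion". The same section asks for listings of excluded participants and of protocol deviations.

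On access to data during the study, SAP 7 says that "the sponsor may conduct unblinded reviews of the data during the course of the study", and Protocol 9.5 gives the purpose as "for the purpose of safety assessment, and supporting clinical development". Neither makes an exception for NT results. For the wider all-available set, which has no violation criterion, Protocol 9.4.1 says: "An additional analysis will be performed based on all-available immunogenicity population if there is enough difference" from the evaluable set.

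**The concern.** Deciding before an analysis is not the same as deciding without knowing the result. Looking up one participant's titre is not an immunogenicity analysis, so a monitor could keep to the SAP's timing and still know who was seronegative. The study is open-label, and the NT laboratory named in Protocol 8.1.1.1 belongs to the sponsor. The only masking statement, in Protocol 8.1.2, keeps participants' identity from laboratory staff and does not mention the monitor.

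The design makes this more sensitive than usual. There is one arm and a fixed 90% bound, so a selective exclusion is not balanced by a similar one in a comparator; it moves the tested proportion directly. The margin is also narrow: the rule tolerates 1 seronegative child in 60 and 3 seronegative adults in 90. With one seronegative too many, regrading one violation would turn a failed objective into a met one. The exclusion listing would show that someone was removed, but not whether the titre was known at the time.

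**Working it through.** **Inputs.** Protocol 9.2: 90 evaluable adults with an assumed rate of 99.4%, and 60 evaluable children with 99.6%. Decision rule (Protocol 9.1, SAP 5.1): the lower limit of the two-sided 95% Clopper-Pearson interval must exceed 90%. One further quantity, *v*, is the probability that a given seronegative participant has a violation open to being graded major. The documents do not give it; I assume 2%, 10% or 20%, independent between participants.

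**1. The plan's own figures.** The rule needs 87/90 (lower limit 90.57%) or 59/60 (91.06%).
- Adults: P(X ≤ 3), X ~ Binomial(90, 0.006) = 99.78%; stated as above 99%.
- Children: P(X ≤ 1), X ~ Binomial(60, 0.004) = 97.57%; stated as 97.3%. The 0.3-point difference does not matter here.

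**2. Effect of one exclusion at the boundary.**

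| Group | One too many | After dropping one seronegative |
|---|---|---|
| Children | 58/60: 88.47%, fail | 58/59: 90.91%, pass |
| Adults | 86/90: 89.01%, fail | 86/89: 90.46%, pass |

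**3. Chance of landing there at the design rates.**
- Children: C(60,2) × 0.004² × 0.996⁵⁸ = 1770 × 0.000016 × 0.7926 = 0.0224.
- Adults: C(90,4) × 0.006⁴ × 0.994⁸⁶ = 2,555,190 × 1.296×10⁻⁹ × 0.5960 = 0.0020.

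**4. Chance that a flip is available.** At least one of the 2 (children) or 4 (adults) seronegatives must also have a gradable violation. Multiply step 3 by 1 − (1 − v)² or 1 − (1 − v)⁴. For v = 20%: children 0.0224 × 0.36 = 0.0081; adults 0.00197 × 0.5904 = 0.0012.

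| v | Children | Adults |
|---|---|---|
| 2% | 0.09% | 0.02% |
| 10% | 0.43% | 0.07% |
| 20% | 0.81% | 0.12% |

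These are maxima, because they suppose that the exclusion is made every time it would help.

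**5. Lower true rates.** At an assumed 99%, step 3 becomes 9.9% and 1.1%; with v = 10% the flip probability is 0.0988 × 0.19 = 1.9% and 0.0108 × 0.3439 = 0.4%. At an assumed 97%, step 3 becomes 27.2% and 15.1%, and v = 10% gives 0.2723 × 0.19 = 5.2% and 0.1508 × 0.3439 = 5.2%. In both cases the true rate is above 90%, so a flip would still lead to the correct statement about the hypothesis.

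**6. False success at a true rate of exactly 90%.** Planned one-sided error plus the chance of being one over times the factor in step 4: children 0.0138 + 0.0393 × [1 − (1 − v)²]; adults 0.0169 + 0.0297 × [1 − (1 − v)⁴].

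| v | Children | Adults |
|---|---|---|
| none (as planned) | 1.4% | 1.7% |
| 2% | 1.5% | 1.9% |
| 10% | 2.1% | 2.7% |
| 20% | 2.8% | 3.4% |
| one seronegative always excludable | 5.3% | 4.7% |

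Setting these equal to the nominal 2.5% gives v of about 15% (children) and 8% (adults). Below those values the conservatism of the exact test absorbs even an exclusion made at every opportunity.

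**7. What an in-study review could show.** The primary titre comes from Visit 5, the last visit (Protocol 1.3). A review during the study could reveal it only for participants who had already finished.

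**The case for a change.** The strongest case for acting is that the remedy looks nearly free. A sentence saying that violations are graded without access to titres would change no sample size, endpoint or safety review, and would make the independence of the exclusions demonstrable. The worst-case figures are also not trivial: if up to two seronegatives could always be dropped, false success at a true rate of 90% would reach 13.7% in children and 10.3% in adults. The all-available analysis cannot be relied on as a check, because what counts as enough difference is not defined.

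Part of this stands. The visible text has no access rule, and one exclusion does decide a boundary result. But the worst-case figures need every seronegative participant to have a real, gradable violation and someone to use it each time. The discretion is narrower than the word opinion suggests, since SAP 4 gives examples tied to immune response and vaccine potency. The stated purpose of the in-study reviews is safety and clinical development, not classification of analysis sets. Text after the main analysis in SAP 6.1.1 is blacked out, so a supportive analysis there cannot be ruled out, and the conditional all-available analysis should not be counted against the plan.

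Nor is the remedy as simple as it looks. Putting an access rule in place of the SAP's timing sentence would remove a safeguard, because others could then run the analysis before the violations were fixed. Changing Protocol 9.5 would mean an amendment and ethics review (Protocol 10.1.1).

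**Conclusion.** The observation is accurate but calls for no change. It is a detail left unwritten, which the sponsor's staff would fill sensibly: the order of work is fixed, the classification is documented, and exclusions are visible with reasons. It is not evidence that titres will be seen; the data handling memo and SOPs may already prevent it.

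At the design rates, a flip could be available with probability at most 0.81% (children) and 0.12% (adults), even at v = 20%. At a true rate of 90%, error passes the nominal 2.5% only if v exceeds about 15% (children) or 8% (adults) and every opportunity is taken. This rests on the planned evaluable numbers, on assumed values of v with independence between participants, on one exclusion per group, and on the SAP's timing being followed. Many violations among seronegative participants would deserve a closer look, and the listings in SAP 6.5.2 would show those that led to exclusion.
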